6.3.1. Exclusion criteria for data encoding

- Subjects who developed a suspected HZ case during ZOSTER-006 and ZOSTER-022 (since their QoL questionnaires were encoded in the eCRF for ZOSTER-006 and ZOSTER-022).

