10.4. Determination of sample size

Approximately 30,000 subjects were enrolled in ZOSTER-006 and ZOSTER-022. Out of these, approximately 1000 subjects will have developed suspected HZ cases over the course of the studies and their QoL questionnaires were encoded in the eCRF for ZOSTER-006 and ZOSTER-022, according to the protocols of those studies, respectively. Therefore approximately 29,000 subjects whose QoL questionnaires were completed and collected but not encoded in the earlier studies, will be encoded in the ZOSTER-064 study. Data encoded as part of the 064 study will be combined with data from the ZOSTER-006 and ZOSTER-022 studies to ensure that subjects data are available for analysis, as appropriate taking into account inclusion/exclusion criteria (see section 6) and cohorts for analysis (see section 10.5).

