10.6. Derived and transformed data

10.6.1. Handling of missing data

For a given subject and a given measurement, missing or non-evaluable measurements will not be imputed for the analysis. The missing endpoint and censoring are supposed to occur independently, and the pattern of the missingness being either Completely At Random (MCAR) or Missing At Random (MAR) only.

For the analysis of solicited symptoms, missing or non-evaluable measurements will not be replaced. Therefore, the analysis of the solicited symptoms based on the TVC will include only subjects/doses with documented safety data (i.e., symptom screen/sheet completed).

For the analysis of unsolicited AEs/SAEs/concomitant medication, all vaccinated subjects will be considered and subjects who did not report an event will be considered as subjects without an event.

For a given subject and a given immunogenicity measurement, missing or non-evaluable measurements will not be replaced. Therefore, an analysis will exclude subjects with missing or non-evaluable measurements.

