5. STUDY POPULATION

5.1. Total Vaccinated cohort

The TVC will include all subjects in the TVC in ZOSTER-006 or ZOSTER-022 who were enrolled at centres participating in ZOSTER-064. All subjects in the TVC in ZOSTER-006 or ZOSTER-022 who were enrolled at centres not participating in ZOSTER-064 will be excluded from the TVC.

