6.3.4. Predictive factors for subjects developing HZ

A Cox regression model allowing for time-dependent covariates will be fitted to identify which factors are predictive of developing HZ. The model will include time to HZ as the outcome variable, the demographic variables age and gender and the time dependent *SF*-36 variables and *EQ-5D* variables as potential predictors. This analysis will be performed for subjects in the Placebo group in the TVC.

Subjects who did not develop HZ will be censored at the time of their last study visit. The regression model will be used for both minimally adjusted analyses and multivariate analyses. All factors will initially be examined in an age- and gender-adjusted model with further adjustment for the original study (ZOSTER-006 or ZOSTER-022). Factors will be included in the multivariate model if they are associated (P < 0.05 using a two-sided Wald test) with HZ in the minimally adjusted model. The multivariate model will also include age, gender and original study. A step-down (backward) variable selection procedure will be used to fit the final multivariate model. This model will be fitted using the PHREG procedure of the SAS/STAT package.

The parameter estimates and standard error of each SF-36 and EQ-5D parameter from the minimally adjusted model will be presented. The final multivariate model will also be presented.

The analysis will be performed with the event defined as a HZ confirmed case. Three separate analyses will be performed examining the impact of excluding suspected but not confirmed cases.

The first analysis will exclude subjects who had a suspected case that was later proven not to be a HZ episode.

204878 (ZOSTER-064) Statistical Analysis Plan Amendment 1

The second analysis will include all subjects. Those subjects who had a suspected case that was later proven not to be a HZ episode will be censored at their latest available assessment and will be considered not to have had the event.

The third analysis will also include all subjects. The definition of event will be changed to having a suspected case of HZ.

The distribution of confirmed cases of HZ amongst suspected cases will be presented by age group for subjects in the placebo group in the TVC.

Details of the process behind the inclusion of time dependent covariates are included in section 7.4

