7.4. Predictive factors for individuals developing HZ

Only subjects in the placebo group will be included in the analysis of potential predictive factors. A Cox regression model allowing for time-dependent covariates will be fitted to identify which factors are predictive of developing HZ. The model will include time to HZ as the outcome variable, the demographic variables age and gender and the *SF-36* variables and *EQ-5D* variables as potential predictors.

Each EQ-5D and SF-36 assessment at a scheduled time point will be re-classified into time points based on the date of assessment relative to date of vaccination:

Studyday=date of assessment – date of vaccination.

The study day will be time component used in the model.

Since there are a maximum of four SF-36 and EQ-5D assessment times we define the variables T_0 , T_1 , T_2 , T_3 as the study day relative to vaccination (day 0) of the QoL assessment and QoL₀ QoL₁, QoL₂, QoL₃ as the values of the QoL assessment at each timepoint. The value of the time-dependent variable QoLt is equal to QoL₀ if $0 < t \le T_1$, QoL₁ if $T_1 < t \le T_2$, QoL₂ if $T_2 < t \le T_3$, with QoLt = QoL₃ if $t > T_3$.

The above model is implemented in SAS as follows:

```
ODS output ParameterEstimates=PE1;

PROC PHREG DATA=tsurv;

CLASS study gender;

MODEL fu_time*hz_conf(0) = age study gender PFT;

PFT=PF0;

IF fu_time > time1 and time1 ne . then PFT=PF1;

IF fu_time > time2 and time2 ne . then PFT=PF2;

IF fu_time > time3 and time3 ne . then PFT=PF3;

RUN;
```

Spearman correlations coefficients will be presented to display the relationships between pairs of variables. In addition, for the quality of life variables, the variance inflation factor and the condition indices for testing multicollinearity will be estimated.

Example: To illustrate the method the following hypothetical 3 subjects are examined:

Table 5 Data from hypothetical subjects to illustrate time dependent covariates

Subject	QoL0	T0	QoL1	T1	QoL2	T2	QoL3	Т3	Censored /day	Event/ day
PPD	80	0	75	425	65	790	24	1050	Yes/1090	No
	90	0	65	420	50	800	45	1050	No	Yes/480
	98	0	43	435	45	790	45	1060	No	Yes/900

204878 (ZOSTER-064)

Statistical Analysis Plan Amendment 1

Table 6 Resolution of hypothetical subject

Subject PPD	Event	Time Interval	QoL
PPD	0	(0, 425]	80
	0	(425, 790]	75
	0	(790, 1050]	65
	0	(1050, 1090]	24

Subject will be censored at day 1090.

Table 7 Resolution of hypothetical subject

Subject	Event	Time Interval	QoL
PPD	0	(0, 420]	90

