9. CHANGES FROM PLANNED ANALYSES

- In the protocol the following secondary objective was intended for baseline only:
 - To present the distribution of SF-36 and EQ-5D scores in subjects included in ZOSTER-006 and ZOSTER-022 at baseline by country to allow comparison with normative values for those questionnaires in the general population of the countries participating in the study.
 - In order to align with the corresponding endpoint, the analysis will be performed at baseline, Months 14, 26 and 38 by country and gender
- The definition of the TVC, mTVC and ATP cohorts have been clarified. In order to minimize bias it was decided that only subjects belonging to centres that participate in ZOSTER-064 will be included. Subjects with data already encoded as part of the ZOSTER-006 or ZOSTER-022 studies will be excluded if the centre to which they belong did not take part in the ZOSTER-064.
- SAEs and pIMDs will not be described in detail as no new safety data was collected in ZOSTER-064 and all SAEs and pIMDs were described in detail in the ZOSTER-006 and ZOSTER-022 CSRs
- Due to the large number of QoL tables generated as a result of the planned analysis by various categories, the key summary tables will be presented as post-text tables in the CSR and more detailed tables will be presented separately in an Annex

204878 (ZOSTER-064) Statistical Analysis Plan Amendment 1

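### If participating centres encode incompletely, only non-cases are lost from the predictive-factor Cox model, and no planned sensitivity analysis would show whether this matters

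*SAP*

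**What the plan says.** Protocol 6.3.1 exempts suspected-HZ subjects from new encoding, "since their QoL questionnaires were encoded in the eCRF for ZOSTER-006 and ZOSTER-022". Everyone else has to be encoded in this study: Protocol 10.4 puts them at "approximately 29,000 subjects whose QoL questionnaires were completed and collected but not encoded in the earlier studies".

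SAP 5.1 restricts the cohort by centre: "The TVC will include all subjects in the TVC in ZOSTER-006 or ZOSTER-022 who were enrolled at centres participating in ZOSTER-064". SAP section 9 gives the reason: "In order to minimize bias it was decided that only subjects belonging to centres that participate in ZOSTER-064 will be included". The current SAP sets no minimum level of encoding for a centre that does participate.

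The Cox model in SAP 6.3.4 uses the placebo group of the TVC and examines each factor in an "age- and gender-adjusted model with further adjustment for the original study (ZOSTER-006 or ZOSTER-022"). Its code in 7.4 reads "MODEL fu_time*hz_conf(0) = age study gender PFT", with no centre or country covariate and no STRATA statement. The three variants in 6.3.4 differ only in how suspected but unconfirmed cases are treated. The bootstrap in Protocol 10.7 concerns variable selection.

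On missing data, Protocol 10.6.1 says that "missing or non-evaluable measurements will not be imputed for the analysis" and takes "the pattern of the missingness being either Completely At Random (MCAR) or Missing At Random (MAR) only". SAP 7.5.2 also rules out imputing questionnaire items. SAP 6.3.1.1 summarises completion by country and overall, with newly and previously encoded forms counted together.

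**The concern.** Every confirmed case was first a suspected case, so the completed forms of cases are already in the database. A form that a site fails to encode always belongs to a subject without suspected HZ. Section 9 of the SAP recognises this selection and removes it where a centre encoded nothing. A centre that encodes half its forms keeps all its cases and loses half of its other subjects, and nothing in the plan addresses that.

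If such centres also have lower (or higher) quality of life than the rest, after age, gender and study, they are over-represented among cases relative to the observed non-cases. The model then reads a difference between centres as an effect of quality of life on HZ. Assuming MAR does not help: availability may depend only on observed suspected-HZ status and centre, but a complete-case model that leaves out centre does not condition on it.

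At stake is the secondary objective of identifying HZ predictors. A factor enters the multivariate model at P < 0.05, so the distortion could admit a false predictor, hide a real one or shrink it.

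**Working it through.** **The plan's own figure.** 30,000 enrolled − about 1,000 suspected = 29,000 to be encoded, which reproduces Protocol 10.4.

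**Availability by outcome.** If a fraction e of non-suspected subjects is encoded, availability is 1 for suspected and e for the others. Pooled completion is (1,000 + 29,000e)/30,000: 90.3%, 80.7% and 51.7% for e = 90%, 80% and 50%.

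**Inputs for the bias**
- From the documents: incidence of 5 to 10 per 1,000 per year (Protocol 1.1.1) and follow-up to Month 38.
- Assumed: 1:1 allocation (15,000 placebo subjects), one third of centres low-encoding, 95% encoding elsewhere, quality of life 0.5 SD lower in low-encoding centres after adjustment, and no true effect.
- Cases: 15,000 × 38/12 × 0.005 = 238, to 15,000 × 38/12 × 0.010 = 475. The main setting of 480 lies just above the top of this range.

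**Closed form.** Among cases, the low-encoding centres keep their share of 1/3. Among observed non-cases their share is s = (e/3) / (e/3 + 0.95 × 2/3). The case-minus-non-case shift is −(1/3 − s) × 0.5 SD, and the null HR per SD is about exp(shift).

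- e = 90%: s = 0.321, shift −0.006, HR 0.994
- e = 70%: s = 0.269, shift −0.032, HR 0.968
- e = 50%: s = 0.208, shift −0.0625, HR 0.939

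With higher quality of life in those centres, the bias would run above 1 instead.

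**Simulation.** Same inputs, 480 cases, 1,000 replicates per setting, SAP model (Monte Carlo error about ±1.4 points at 5% and ±2.7 at 25%):

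| Encoding in low centres | HR per SD | Type I error |
|---|---|---|
| 90% | 0.995 | 4% |
| 80% | 0.985 | 7% |
| 70% | 0.97 | 10% |
| 50% | 0.945 | 25% |

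**Sensitivity to the assumptions**
- 0.3 SD gap: type I error 7% at 70% encoding and 13% at 50%.
- 240 cases, 0.5 SD gap: 8% at 70% and 18% at 50%. With 0.3 SD: 7% at 50%.
- No gap, even at 40% encoding: HR 1.00, 6%.
- A true HR of 1.10 running against the bias reads 1.07 at 70% and 1.04 at 50%.

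**Does stratifying help?** Strata of study by centre give 4–7% error in all the null settings above, with a 2–5% larger standard error. Country strata at 50% encoding give 25% if the low centres are spread over countries, and 5% only if low encoding follows country. If encoding depends on a subject's own quality of life within a centre (odds 1.35 per unit, 70% in low centres, no gap between centres), the error is 11% without centre strata and 13% with them, so they do not help there.

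**What the planned completion table would show.** Take a country with 3 of 10 equal centres at 50% and the rest at 95%. Non-suspected completion is 0.3 × 50% + 0.7 × 95% = 81.5%. Pooled completion is 1/30 + (29/30) × 0.815 = 82%. The shortfall is visible, but not which centres cause it.

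**The case against.** The strongest reply is that no document shows the premise. Bias needs three things together: partial encoding, encoding that differs between centres, and low encoding that goes with residual quality of life. The protocol aims at complete data: all questionnaires (6.1), subject lists issued to sites (8.1), investigator review (8.3.4) and source verification (11.2). Every input that drives the size is assumed. The analysis is secondary, without multiplicity control, and Protocol 10.8 asks for caution. All of this stands, and it keeps the point minor and conditional. Completeness is still an aim rather than a result, and the SAP itself provides for a completion table and an Unknown frailty group.

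Some of the needed display is already planned. SAP 6.3.3 tabulates confirmed cases and follow-up time by frailty category, and Table 1 defines an Unknown category. By-centre layouts may also be in the TFL annex, which is not among the documents available. Both limit the remedy.

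A reader might infer that the current SAP is at fault for lacking the rule in the November 2018 SAP that excluded centres encoding under 50%. That text is superseded and the difference is not an error. It shows only that poor encoding had been foreseen.

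**Conclusion.** The point holds in conditional form. The route by which encoding gaps would remove only non-cases is in the current documents, and no planned analysis tests it within participating centres. Under the assumptions listed, the distortion is negligible at about 90% encoding or with no quality-of-life gap, modest near 70%, and potentially material at 50% or below. With fewer cases or a smaller gap, the false-positive rate is lower.

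Two stronger readings are tempting and unsupported. One is that encoding was in fact incomplete or that the planned results are biased; the documents give no encoding rates and no link between encoding and quality of life. The other is that availability depending on outcome is enough by itself to bias the hazard ratio; with no gap the model returns 1.00. The supported conclusion is narrower: the plan lacks a simple check that would separate a centre-level encoding artefact from a predictor. It is a minor, cheap improvement.

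**What to change.** - **SAP 6.3.4 and 7.4:** keep the planned model as the main analysis. Add one sensitivity model with the same covariates, stratified by study and centre through a STRATA statement. Country strata alone are not enough if low encoding arises at centre level.
- **SAP 6.3.1.1:** show completion by centre, separately for suspected and non-suspected subjects, unless the TFL already does so.
- **SAP 6.3.3:** make sure the Unknown row is printed in the table already planned. An Unknown group with almost no cases would be a warning sign. For example, at 70% in low centres mean encoding is 0.7/3 + 0.95 × 2/3 = 86.7%, so 15,000 × (29/30) × (1 − 0.867) gives about 1,930 placebo subjects in that row. None would be a confirmed case if all suspected subjects' forms are complete, against about 62 expected at an assumed 3.2% risk. No new display in 6.3.2 is needed.
- **Limits to state:** centre strata do not correct encoding that depends on a subject's own quality of life within a centre.

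Excluding centres below an encoding threshold is optional. The cut-off is a judgement, and dropping one third of centres lowers simulated power for an HR of 1.10 from 57% (full encoding) to 39%.

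Cost: one extra model run with a 2–5% larger standard error, and one table split, all from data already held. The main model is unchanged.

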5. HZ CASE DEFINITION

Classification as a HZ confirmed case was done during ZOSTER-006 and ZOSTER-022, after confirmation of all suspected HZ cases by either of the two following ways:

- Polymerase Chain Reaction (PCR):
Rash lesion samples were collected from subjects clinically diagnosed as having a suspected case of HZ. The samples were transferred to GSK Biologicals or a validated laboratory designated by GSK Biologicals using standardised and validated procedures for laboratory diagnosis of HZ by PCR. For more information, please refer to Appendix B of the ZOSTER-006 protocol.
- The HZ Ascertainment Committee:

All suspected HZ cases were referred to the HZ Adjudication Committee (HZAC). The HZAC classified all referred cases as either “HZ”, “not HZ”, or “not able to decide”. However, the HZAC classification was to serve as the final case definition only when the case could not be confirmed or excluded by PCR, e.g., when all samples from a given subject were inadequate (as when both VZV and β -actin PCR results were negative), or when no samples were available for a given subject. If the case could not be confirmed or excluded by PCR and the HZAC final outcome was ‘not able to decide’, the overall final outcome was “No possible classification”; for analysis the categories “not HZ” and “No possible classification” were considered as “not HZ”.

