10.7.6.3. Predictive factors for individuals developing HZ

Only subjects in the placebo vaccination group will be included in the analysis of potential predictive factors. A Cox proportional hazards regression model allowing for time-dependent covariates will be fitted to identify which factors are predictive of developing HZ. The model will include time to HZ as the outcome variable and as potential predictors: demographic and clinical characteristics, *SF-36* variables and *EQ-5D* variables. Subjects who did not develop HZ will be censored at the time of their last study visit. The proportional hazards regression model will be used for both minimally adjusted analyses and multivariate analyses. All factors will initially be examined in an age- and sex-adjusted model with stratification for the clinical trial (i.e. ZOSTER-006 and ZOSTER-022). Factors will be included in the multivariate model if they are associated ($P < 0.05$ using a two-sided test) with HZ in the minimally adjusted model. The multivariate model will also include age and gender with stratification for the clinical trial (i.e. ZOSTER-006 and ZOSTER-022). A step-down (backward) variable selection procedure will be used to fit the final multivariate model. This model will be fitted using the PHREG procedure of the *SAS/STAT* package.

Spearman correlations coefficients will be presented to display the relationships between pairs of variables. In addition, particularly for the quality of life variables, the variance inflation factor and the condition indices for testing multicollinearity will be estimated.

In the analysis, the impact of excluding “suspected but not confirmed cases” of HZ will be explored. Three analyses will be performed whereby it will be assumed that “suspected but not confirmed cases” are (1) “Not in at risk group” (2) “In at risk group” and event=0, (3) “In at risk group” and event=1.

Due to the multiple measurements of the *EQ-5D* and *SF-36* over time, repartition in the HZ positive or HZ negative will be dynamic. Subjects who did not develop a confirmed HZ before one-timepoint (Day 0, Month 14, Month 26 and Month 38) will be considered HZ negative at that timepoint, and the characteristics and QoL scores reported for this subject at the previous timepoint will be considered as **not leading** to HZ.

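### SAP 6.3.4 sets analyses 1 and 2 by any ruled-out suspected case, so as written a subject who also has a confirmed HZ would be excluded or coded as a non-event, and unclassifiable cases are handled ambiguously

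*SAP*

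**What the plan says.** SAP 6.3.4 (Amendment 1) fits a Cox model in the placebo group of the TVC. It fixes the outcome first: "The analysis will be performed with the event defined as a HZ confirmed case". It then announces three runs to examine the effect of excluding suspected but not confirmed cases.

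- Analysis 1: "The first analysis will exclude subjects who had a suspected case that was later proven not to be a HZ episode".
- Analysis 2 keeps everyone, but those who meet the same trigger "will be censored at their latest available assessment and will be considered not to have had the event".
- Analysis 3: "The definition of event will be changed to having a suspected case of HZ".

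Protocol 10.7.6.3 sets the purpose: "In the analysis, the impact of excluding" suspected but not confirmed cases is to be explored. It takes that whole class as (1) outside the risk set, (2) at risk without an event, or (3) at risk with an event. The same section treats any subject with a confirmed HZ between two timepoints as HZ positive at the later one, and censors QoL scores recorded after onset.

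Protocol section 5 gives three final outcomes for a suspected case. The third is reached as follows: "If the case could not be confirmed or excluded by PCR and the HZAC final outcome was" undecided, the case receives no possible classification. The section adds that, for analysis, this category and the not-HZ category were both considered not HZ.

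**The concern.** Case status belongs to an episode, and one subject can have more than one suspected episode. The SAP rules for analyses 1 and 2 are set off by the presence of any ruled-out episode and then decide the status of the whole subject. A placebo subject with a ruled-out rash and, at another time, a confirmed HZ meets the event definition and also meets the trigger for removal or for event = 0. The text does not say which prevails, and the literal rule sides with the trigger.

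The trigger also requires that a case was proven not to be HZ. Protocol 10.7.6.3 and the SAP's own lead-in refer to suspected but not confirmed cases, which is wider. Cases with no possible classification lie in the gap.

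Predictors of HZ are a named secondary objective, and these runs are the planned check on case ascertainment. Factors enter the multivariate model on P < 0.05 in the minimally adjusted model, so event status feeds into which factors are considered. Two programmers could build different analysis sets from this text.

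**Working it through.** The documents state no event count or power for this analysis, so there is no planned figure to reproduce. The check applies the three SAP rules, as written, to each possible episode history. N is ruled out, C is confirmed and U is no possible classification. The strict reading takes proven not as N only. The mapped reading carries over Protocol section 5, so that U counts as N.

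| History | Reading | Analysis 1 | Analysis 2 | Analysis 3 |
|---|---|---|---|---|
| None | both | in, event 0 | in, event 0 | in, event 0 |
| N only | both | excluded | in, event 0 | event |
| C only | both | event | event | event |
| N then C | both | **excluded** | **in, event 0** | event |
| C then N | both | **excluded** | **in, event 0** | event |
| U only | strict | in, event 0 | in, event 0 | event |
| U only | mapped | excluded | in, event 0 | event |
| U then C | strict | event | event | event |
| U then C | mapped | **excluded** | **in, event 0** | event |

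Three things follow.

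1. With both N and C, in either order, the confirmed HZ disappears from analyses 1 and 2 under both readings. In the C-then-N order, an observed event is undone by something that happened later. Analysis 2 then follows the subject to the latest assessment, so QoL scores after onset would enter the model although Protocol 10.7.6.3 censors them.
2. For U only, analysis 1 depends on the reading. Analysis 2 does not, and event = 0 there is what protocol option (2) asks for.
3. The mapped reading settles U only in line with the protocol, but it extends the lost-event problem to U with C.

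**Size.** The only relevant count is in Protocol 10.4: about 1000 subjects with a suspected case, both arms together. The split by arm, by outcome and by number of episodes is not given. All shares below are assumptions.

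- Placebo subjects with a suspected case: assume 600 to 1000 (1000 is the ceiling).
- Share with both a ruled-out and a confirmed episode: assume 0.5% to 5%. Affected: 600 × 0.005 = 3, up to 1000 × 0.05 = 50.
- Share unclassifiable: assume 1% to 10%. Affected: 600 × 0.01 = 6, up to 1000 × 0.10 = 100. Against an assumed 15,000 placebo subjects (half of 30,000), 100 is 100 / 15,000 = 0.67%.

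**Power if events are lost.** Schoenfeld approximation, binary factor split 50:50, assumed HR 1.25, two-sided 0.05: power = Φ(ln 1.25 × √(D/4) − 1.96), where D is the number of events.

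| Events before loss (assumed) | No loss | 2% lost | 5% lost |
|---|---|---|---|
| 500 | 0.7036 | 0.6949 | 0.6814 |
| 800 | 0.8841 | 0.8778 | 0.8678 |

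The smallest drop is 0.8841 − 0.8778 = 0.0063 and the largest is 0.7036 − 0.6814 = 0.0222, so about 0.6 to 2.2 points.

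**The case against.** The best defence is that other text shows what was meant. The event is confirmed HZ, and the general censoring rule in SAP 6.3.4 is for subjects who did not develop HZ. The SAS code in SAP 7.4 uses a flag named hz_conf, and a person with confirmed HZ is not naturally a suspected but not confirmed case. No passage says that anyone had both kinds of episode. The analysis is exploratory, and Protocol 10.8 asks for cautious, descriptive interpretation.

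Much of this stands as evidence of intent and as a limit on size, but it does not repair the rules. Analysis 1 removes the subject before any event flag is read, the derivation of hz_conf is not shown, and analysis 2 states the event status of these subjects outright.

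A reader might infer three stronger things that the documents do not support.

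- *That confirmed cases are in fact lost.* This holds only if subjects with both kinds of episode exist, and the documents do not say.
- *That unclassifiable cases stay in analysis 1 as non-events.* Protocol section 5 counts them as not HZ for analysis, and the SAP's lead-in keeps the wider class. The text is ambiguous rather than clearly wrong.
- *That analysis 3 is an error because it counts ruled-out rashes as events, or that a further run must isolate the unclassifiable cases.* Analysis 3 carries out protocol option (3), an extreme assumption set against event = 0 in analysis 2. A further run would be a preference.

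**Conclusion.** The point holds as a defect of wording with a definite consequence for one kind of history. A placebo subject with both a ruled-out episode and a confirmed HZ gets the wrong status in analyses 1 and 2 if the SAP is programmed as written, contrary to the SAP's event definition and to Protocol 10.7.6.3. Separately, the narrower trigger leaves unclassifiable cases ambiguous in analysis 1, and SAP section 9 does not list any departure from the protocol here. Analysis 3 is sound.

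The number of subjects affected cannot be derived from the documents. The assumed ranges suggest a small effect, and nothing shows that the selected predictors would change. The case for acting is that the contradiction is plain and the repair is cheap.

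**What to change.** Amend SAP 6.3.4 in two places.

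- Replace the proven-not trigger in analyses 1 and 2 with the protocol's class, suspected but not confirmed, and say that it includes cases with no possible classification, as Protocol section 5 treats them.
- Add a sentence such as: *In analyses 1 and 2 a subject's first confirmed HZ is always the event, whatever other suspected episodes the subject had; the rules for suspected but not confirmed cases apply only to subjects without a confirmed HZ.*

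Derive the event flag and the analysis 1 exclusion accordingly. If the sponsor does intend the narrower trigger, list it in SAP section 9 with the reason.

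The cost is a short SAP text change and a revised flag. The outcome classes were assigned in the parent studies, so no new data are needed. Analysis 3 stays as it is, and no extra model run is required.
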